8.3.4 Additional Analyses of the Primary Efficacy Endpoint

For the primary efficacy endpoint, a supplementary analysis will be based on treatment policy estimand framework using the same CMH method using AO data. The attributes of the corresponding estimand are outline in [Appendix D](#).

For the treatment policy estimand, additional supplementary analysis will be conducted using AO with imputation. The same CMH method will be conducted.

Additional supplementary analysis using MI as outlined in Section 8.2 based on AO data, i.e., all observed data regardless of study drug adherence or initiation of rescue or concomitant medications for PsA that could meaningfully impact efficacy assessment, will also be conducted to handle missing ACR20 responses. To assess the deviation from missing at random (MAR) assumption, tipping point analysis will be conducted as a sensitivity analysis for this supplementary analysis. Details of the analysis are outlined in [Appendix F](#).

8.4 Secondary Efficacy Analyses

8.4.1 Secondary Efficacy Analyses

The secondary endpoints are defined in Section 3.2. Ranked secondary endpoint will be tested in rank order, according to procedures in Section 12.0.

For all binary secondary endpoints, frequencies and percentages will be reported for each treatment group. The primary estimand and analysis method are the same as that for the primary efficacy endpoint as defined in Section 8.3.4. NRI-C missing data handling will be used to analyze the primary estimand (refer to [Appendix D](#)).

For the secondary endpoints applicable only for a sub-population, the estimand will be constructed similarly but based on the sub-population, as defined in the below table.

Endpoint	Sub-population
Psoriasis Area Severity Index (PASI) 90 response at Week 24	Subjects with BSA $\geq 3\%$ at baseline are included in the analysis
Resolution of enthesitis (LEI = 0) at Week 24	Subjects with baseline presence of enthesitis (LEI > 0) are included in the analysis
Resolution of dactylitis (LDI = 0) at Week 24	Subjects with baseline presence of dactylitis (LDI > 0) are included in the analysis

For continuous secondary efficacy variables, primary analysis will be based on the hypothetical estimand. The attributes of the corresponding estimand are outline in [Appendix D](#). The comparison is risankizumab 150 mg vs placebo for patients randomized and treated with at least one dose of study drug. Statistical inference will be conducted using the MMRM model and the associated data handling as described in Section 8.2. The least square (LS) mean and 95% CI for each randomized treatment group and the LS mean treatment difference, the associated 95% CI and the p-value between risankizumab 150 mg group and the placebo group will be provided.

8.4.2 Supportive Secondary Efficacy Analyses

For all binary secondary endpoints, the same CMH analyses as the supplementary analyses will be conducted using AO data and AO with imputation. The corresponding supplementary estimand is the same as defined in Section 8.3.4 except for the definition of the efficacy measurement (refer to [Appendix D](#)).

For continuous secondary endpoints, supplementary analyses on the FAS will be performed based on AO data using the treatment policy estimand framework (refer to [Appendix D](#)). The statistical inference will be conducted using ANCOVA model including treatment as the fixed factor and the corresponding baseline value and the stratification factor as the covariates. The LS mean and 95% CI will be reported for each randomized treatment group; the LS mean treatment difference and associated 95% CI and p-value will be reported comparing risankizumab 150 mg with the placebo group.

For HAQ-DI at Week 24, additional supplementary analysis will be conducted using MI as outlined in Section 8.2 based on AO data under MAR assumption. To assess deviations from MAR, the tipping point analysis will also be conducted using MI as additional sensitivity analyses. Details of the MI and tipping point analysis are outlined in Appendix F.

8.5 Additional Efficacy Analyses

Additional endpoints defined in Section 3.3 will be analyzed in at scheduled time points other than those specified for the primary and key secondary variables.

Additional Efficacy Analyses for Period 1

Additional endpoints will be analyzed for each randomized treatment group for all visits.

For binary endpoints, point estimate and 95% CI using normal approximation will be provided for the response rate for each randomized treatment group. Point estimate, 95% CI and p-value will be provided for the treatment comparison between risankizumab 150 mg and the placebo group based on the CMH test adjusting for stratification factors. Only the nominal p-value will be provided. NRI-C for missing data handling will be used. AO analysis will be used as supplementary analysis.

For continuous endpoints, the LS mean and 95% CI will be reported for each randomized treatment group. The LS mean treatment difference and associated 95% CI and p-values between risankizumab 150 mg and the placebo group will be provided using MMRM model. Only the nominal p-value will be provided. Data observed after initiation of rescue or concomitant medications for PSA that could meaningfully impact efficacy assessment will be excluded. Supplementary analysis will be conducted based on ANCOVA model using AO data, with treatment and stratification factors as the fixed factors and the corresponding baseline value as the covariates. Nominal p-values will be provided.

For HRU related endpoints, number and percentage of subjects with non-study health visits will be provided by visit and over the double-blind period up to Week 24. In addition, cumulative number of utilizations per time (e.g., subject-year) up to Week 24 will be provided for each category.

Long-Term Efficacy Analyses

Assessments to evaluate long-term efficacy will be analyzed for all efficacy measurements at scheduled visits.

Descriptive statistics will be provided for each randomized treatment sequence as defined in Section 8.1. These include the number of observations, mean, standard deviation, 95% CI, median, minimum, and maximum for continuous endpoints, and frequencies and percentages with 95% CI using normal approximation for binary endpoints. Plot for each randomized treatment group sequence over time will be provided for primary and multiplicity-controlled secondary endpoints and selected additional endpoints. These efficacy analyses will be based on AO analysis.

A similar analysis for HRU endpoints will be provided at Week 52.

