In the Phase 2 study of risankizumab in subjects with PsA (Study M16-002), 4 risankizumab dosing regimens were evaluated: single dose of 75 mg at Week 0 (N = 20); 150 mg at Week 0 and 12 (N = 39); 150 mg at Week 0, 4, and 16 (N = 42); and 150 mg at Week 0, 4, 8, 12, and 16 (N = 42). In this study, risankizumab-treated subjects demonstrated significant improvement compared to placebo in key rheumatology endpoints (ACR20/50/70 and DAS28-CRP) and skin-related endpoints (PASI 75/90/100). At Week 16, ACR20/50/70 responses were 62%/24%/7% in subjects who received risankizumab doses of 150 mg SC at Weeks 0, 4, and 16 compared to 36%/12%/0% in subjects on placebo. The Week 16 PASI 75/90/100 responses, in subjects with baseline BSA of skin symptoms \geq 3%, were 70%/67%/50% in

subjects who received risankizumab doses of 150 mg SC at Weeks 0, 4, and 16 compared to 10%/10%/10% in subjects on placebo. No further improvements in ACR or PASI responses were noted in subjects who received risankizumab doses of 150 mg at Weeks 0, 4, 8, 12, and 16.

Risankizumab exposures in subjects with PsA in the Phase 2 study (Study M16-002) were comparable to those in subjects with PsO in Phase 1 through 3 studies at similar dose and dosing frequency. The ADA incidence (approximately 12% [17/140] over 32 weeks) in risankizumab-treated subjects with PsA (Study M16-002) was comparable to that in subjects with PsO or CD, and presence of ADA did not affect risankizumab plasma exposures.

Exposure-response analyses were conducted to explore the relationship between risankizumab C_{avg} (the average plasma concentration from Week 0 – 16) and ACR20/50/70 and PASI 75/90/100 responses at Week 16 in subjects with PsA (Study M16-002). For this analysis, C_{avg} from Weeks 0 to 16 was used as an exposure metric, as it accounts for the differences in risankizumab dosing frequency across different arms in the study. A shallow trend for exposure-response relationship was observed for ACR20, PASI 75, and PASI 90 across the risankizumab regimens evaluated in the Phase 2 study.

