5.8 Randomization/Drug Assignment

All subjects will be assigned a unique identification number by the IRT at the Screening Visit. For subjects who rescreen, the screening number assigned by the IRT at the initial Screening Visit should be used. Subjects will be randomized in a 1:1 ratio to one of two treatment groups:

- Group 1: Risankizumab 150 mg (N = 210)
- Group 2: Placebo (N = 210)

Randomization will be stratified by current use of csDMARD (0 vs ≥ 1), number of prior biologic therapies (0 vs ≥ 1), and extent of psoriasis ($\geq 3\%$ BSA or $< 3\%$ BSA) at Baseline.

The Investigator, study site personnel, and the subject will remain blinded to each subject's treatment in Period 1 throughout the study. AbbVie will carry out an analysis of the primary endpoint at Week 24. To maintain the blind during the blinded portion of the study, the risankizumab pre-filled syringe (PFS) and placebo PFS provided for the study will be identical in appearance.

In the event of a medical emergency in which the Investigator believes that knowledge of study drug treatment is required, reasonable efforts must be made to contact the AbbVie Emergency Contact prior to breaking the blind, as long as it does not compromise subject safety. However, if an urgent therapeutic intervention is necessary which warrants breaking the blind prior to contacting AbbVie Emergency Contact, the Investigator can directly access the IRT system to break the blind without AbbVie agreement.

The date and reason that the blind was broken must be recorded in the source documentation and eCRF, as applicable.

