3.2 Secondary Endpoints

The following is a list of ranked secondary endpoints with multiplicity adjustment:

1. Change from Baseline in Health Assessment Questionnaire-Disability Index (HAQ-DI) score at Week 24;

2. Psoriasis Area Severity Index (PASI) 90 response at Week 24 (for subjects with BSA \geq 3% at Baseline);
3. ACR20 response at Week 16;
4. Minimal Disease Activity (MDA) response at Week 24;
5. Change from baseline in 36-Item Short Form Health Survey (SF-36) Physical Component Summary (PCS) score at Week 24;
6. Change from baseline in Functional Assessment of Chronic Illness Therapy-Fatigue (FACIT-Fatigue) score at Week 24.

Other secondary endpoints are:

1. ACR50 response at Week 24;
2. ACR70 response at Week 24;
3. Resolution of enthesitis defined as Leeds Enthesitis Index (LEI = 0) at Week 24 (for subjects with baseline presence of enthesitis (LEI > 0));
4. Resolution of dactylitis defined as Leeds Dactylitis Index (LDI = 0) at Week 24 (for subjects with baseline presence of dactylitis (LDI > 0)).

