3.3 Additional Efficacy Endpoints

The primary and secondary efficacy endpoints are listed in Section 3.1 and Section 3.2, respectively. Additional efficacy endpoints at all scheduled visits (when measurements are collected) are listed below.

- ACR20/50/70 response;
- Change from Baseline in individual components of ACR response:
 - Change from Baseline in Tender Joint Count (TJC) (0 - 68);
 - Change from Baseline in Swollen Joint Count (SJC) (0 - 66);

- Change from Baseline in Physician Global Assessment of Disease Activity (PGA) (mm on a 100-mm horizontal visual analogue scale [VAS]);
- Change from Baseline in Patient's Global Assessment of Disease Activity (PtGA) (mm on a 100-mm horizontal visual analogue scale [VAS]);
- Change from Baseline in Patient's Assessment of Pain (mm on a 100-mm horizontal visual analogue scale [VAS]);
- Change from Baseline in Health Assessment Questionnaire - Disability Index (HAQ-DI) score;
- Change from Baseline in High-Sensitivity C Reactive Protein (hs-CRP);
- MDA response;
- Change from Baseline in LDI (for subjects with Baseline LDI > 0);
- Change from Baseline in dactylitis count (for subjects with Baseline LDI > 0);
- Resolution of dactylitis (LDI = 0) (for subjects with Baseline LDI > 0);
- Change from Baseline in LEI (for subjects with Baseline LEI > 0);
- Resolution of enthesitis (LEI = 0) (for subjects with Baseline LEI > 0);
- Change from Baseline in Spondyloarthritis Research Consortium of Canada (SPARCC) Enthesitis Index (for subjects with baseline SPARCC Enthesitis Index > 0);
- Resolution of enthesitis sites included in the SPARCC Enthesitis Index (for subjects with Baseline SPARCC Enthesitis Index > 0);
- Change from Baseline in total enthesitis count (for subjects with baseline LEI > 0 and Baseline SPARCC Enthesitis Index > 0);
- Resolution of enthesitis in both LEI and SPARCC (defined as LEI = 0 and SPARCC = 0) (for subjects with Baseline LEI > 0 and Baseline SPARCC Enthesitis Index > 0);
- PASI 75/90/100 response (for subjects with BSA \geq 3% at Baseline);
- Achievement of both PASI 90 and ACR50 (for subjects with BSA \geq 3% at Baseline);
- Change from Baseline in BSA-PsO (for subjects with BSA \geq 3% at Baseline);
- Modified Psoriatic Arthritis Response Criteria (PsARC);

- Change from Baseline in Disease Activity Score 28 using high sensitivity C Reactive Protein (DAS28-hsCRP);
- Change from Baseline in PsA Disease Activity Score (PASDAS);

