8.3.3 Primary Efficacy Analysis

Analysis of the primary endpoint will be conducted on the FAS based on randomized treatment groups (risankizumab 150 mg versus placebo) using NRI-C for missing data handling. Point estimate and 95% CI using normal approximation will be provided for the response rate for each randomized treatment group. Comparison of the primary endpoint between the risankizumab and placebo groups will be made using the CMH adjusting for stratification factors. Point estimate, 95% CI and nominal p-value for the treatment difference will be presented. Refer to [Appendix E](#) for the details of NRI-C procedure and respective statistical inference.

A sensitivity analysis will be conducted on the Per Protocol Analysis Set using the CMH model and NRI-C missing data handling.

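### Normal-approximation intervals for single-arm response rates have no fallback for sparse counts, which matters for placebo ACR70 and similar near-empty cells

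*SAP*

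**What the plan says.** SAP Section 8.5 sets the interval for each arm's response rate in Period 1: "For binary endpoints, point estimate and 95% CI using normal approximation will be provided for the response rate for each randomized treatment group". For the long-term tables the same section asks for "frequencies and percentages with 95% CI using normal approximation for binary endpoints". Neither place provides an exact, Wilson or other interval for zero or small counts.

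The endpoints covered are those of SAP Section 3.3, which says: "Additional efficacy endpoints at all scheduled visits (when measurements are collected) are listed below". That list includes "ACR20/50/70 response". The Operations Manual (Section 2.1) collects every ACR component from Week 4, and SAP Appendix E lists binary endpoints at Weeks 4, 8, 12, 16 and 24. ACR70 is therefore tabulated by arm from Week 4.

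ACR70 at Week 24 is also an unranked secondary endpoint (SAP Section 3.2). Whether it receives a single-arm interval is not clear. Section 8.4.1 asks for frequencies and percentages by group. It then refers to Section 8.3.4 for the method, and that section contains no single-arm interval. Section 8.3.3, on the primary endpoint, does contain one.

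On expected rates, Protocol Section 4.2 gives Week 16 ACR20/50/70 in the Phase 2 study for the regimen of 150 mg at Weeks 0, 4 and 16, "compared to 36%/12%/0% in subjects on placebo".

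**The concern.** The normal-approximation (Wald) interval takes its standard error from the observed proportion. When that proportion is zero the standard error is zero, and the interval shrinks to a point. When the proportion is small but positive, the symmetric interval runs below zero. In both cases actual coverage can be far below the nominal 95%.

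The sponsor's own Phase 2 placebo figure for ACR70 makes such a cell a realistic prospect in this trial, above all at the early visits. A printed 95% interval of 0% to 0% claims a certainty that 210 subjects cannot give. A negative limit is an impossible value, and the SAP has no rule for presenting it. What is at stake is the accuracy of error bars in descriptive tables, not a test.

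**Working it through.** **Inputs.**
- Arm size n = 210 (Protocol Section 5.8).
- Interval method: normal approximation (SAP Section 8.5).
- Phase 2 placebo ACR70 at Week 16: 0% (Protocol Section 4.2).
- Assumed: the true placebo ACR70 rate in this trial, which the documents do not give. A range is shown.

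The plan states no figure for the interval itself, so there is none to reproduce. The denominator of 210 comes from the sample-size calculation, which does reproduce: with 10% dropout, 189 per arm gives 89.8% power for the HAQ-DI difference of 0.24 with SD 0.72, against the stated approximately 90%.

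**Formulas**, with p = x/n and z = 1.96:
- Wald: p ± z·√(p(1−p)/n)
- Wilson: [p + z²/(2n) ± z·√(p(1−p)/n + z²/(4n²))] / (1 + z²/n)
- Clopper-Pearson: exact limits from beta quantiles

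**Intervals at n = 210.**

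| Responders | Wald | Wilson | Clopper-Pearson |
|---|---|---|---|
| 0 | 0 to 0% | 0 to 1.80% | 0 to 1.74% |
| 1 | −0.45 to 1.41% | 0.08 to 2.65% | 0.01 to 2.62% |
| 2 | −0.36 to 2.27% | 0.26 to 3.41% | 0.12 to 3.40% |
| 3 | −0.18 to 3.03% | 0.49 to 4.12% | 0.30 to 4.12% |
| 4 | 0.06 to 3.75% | 0.74 to 4.79% | 0.52 to 4.80% |

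The Wald lower limit is negative when 0 < p < z²/(n + z²) = 3.84/213.84 = 1.80%, that is, at 1 to 3 responders.

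**Exact coverage at n = 210**, summing binomial probabilities over every x whose interval contains the true rate. The last column is the chance of 0 to 3 responders, hence of a zero-width interval or a negative limit.

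| True rate | Wald | Wilson | Chance of 0 responders | Chance of 0 to 3 responders |
|---|---|---|---|---|
| 0.5% | 65.0% | 97.8% | 35% | 98% |
| 1% | 87.7% | 93.9% | 12% | 84% |
| 2% | 92.0% | 95.9% | 1.4% | 39% |
| 3% | 94.8% | 96.2% | 0.2% | 12% |
| 5% | 94.4% | 94.5% | under 0.1% | 0.6% |
| 35.7% | 94.6% | 94.8% | 0 | 0 |

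**Smaller denominators.** If 10% of subjects are missing from an As Observed table (n = 189), Wald coverage is 61%, 85% and 89% at true rates of 0.5%, 1% and 2%, then 92% at 3% and 91% at 5%. For an assumed subset of 105 it is 65% at 1% and 82% at 3%.

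**The case against.** The strongest reply is that these are descriptive single-arm intervals printed beside counts and percentages, so a reader can see that a 0-to-0 interval is degenerate. Treatment effects come from the stratified CMH risk difference, ACR70 is unranked, and no error control uses these limits. All of that stands, and it keeps the point minor.

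Four stronger readings are tempting, and the documents do not support them.

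- **That ACR50, MDA and PASI 90/100 are equally affected.** Phase 2 placebo ACR50 was 12% and PASI 75/90/100 was 10% each at Week 16. At n = 210 Wald coverage is 93.7% at 12% and 95.3% at 10%. PASI is analysed only in subjects with BSA of at least 3%, so n = 210 does not apply to it. No MDA rate is given, and MDA at Weeks 4 and 8 is doubtful because the Operations Manual schedules no enthesitis assessment then. Only placebo ACR70 has direct documentary support; other early-visit cells may be sparse but are not quantified.
- **That the Phase 2 0% proves a true rate near zero.** The Phase 2 placebo group size is not stated. If it was 42 (an assumption, consistent with 15/42 = 35.7% and 5/42 = 11.9%), the exact upper limit for 0 of 42 is 1 − 0.025^(1/42) = 8.4%. True rates of 3% to 5%, where Wald performs acceptably at n = 210, are not excluded.
- **That Section 8.3.3 needs the same repair.** It concerns ACR20, planned at a placebo rate of 35.7%, where Wald coverage is 94.6%.
- **That Wilson or Clopper-Pearson can be substituted everywhere at no cost.** NRI-C rates in Period 1 come from 30 imputed datasets, so there is no single responder count. Appendix E gives Rubin pooling only for the treatment difference.

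**Conclusion.** The point holds in a narrow form. Section 8.5 fixes an interval method that fails for rare responses and offers no alternative, although the protocol itself reports a 0% placebo ACR70 rate. At n = 210 the failure needs 0 to 3 responders, or a true rate of about 2% or less. Coverage there is about 65% at 0.5%, 88% at 1% and 92% at 2%; at 3% and 5% it is 94% to 95%.

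This rests on two assumptions: that some placebo ACR70 cells, most plausibly at early visits, will have true rates in that range, and that the denominator is close to 210. Smaller denominators extend the problem to somewhat higher rates. No comparison, ranked endpoint or error control is touched, so the severity is low.

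**What to change.** Amend SAP Section 8.5 in three respects.

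1. In the As Observed and long-term tables, use Wilson intervals (or Clopper-Pearson) for single-arm response rates.
2. In the NRI-C tables, use a Wilson interval adapted to multiple imputation, built from the Rubin-pooled proportion and variance. State that it reduces to the ordinary Wilson interval when all imputed datasets agree, including when every one has zero responders and the pooled variance is zero.
3. State whether ACR70 at Week 24 receives a single-arm interval under Section 8.4.1, and if so apply the same rule.

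The ACR20 interval in Section 8.3.3 can stay as it is. No estimand, test or sample size changes. For the As Observed and long-term tables the cost is SAP wording and a program option; the NRI-C tables need a small amount of extra programming. Some wording for those tables is needed in any case, because pooling of the single-arm interval is not specified at present.

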8.6 Efficacy Subgroup Analyses

The primary efficacy endpoint will be examined in the subgroups listed in [Table 1](#) below. Treatment difference between risankizumab 150 mg and the placebo group in each category of a subgroup will be presented with point estimate and 95% confidence interval using CMH test adjusting for stratification factors. No p-value will be provided for subgroup analysis. Forest plots presenting the treatment effect of all categories of subgroups will be provided.

Table 1. Subgroups for Efficacy Analysis

Subgroup Factor	Categories
Age	< 65 years, ≥ 65 years, ≥ 65 - < 75 years, ≥ 75 years
Sex	Male vs Female
BMI	< 25, ≥ 25 and < 30, ≥ 30 kg/m ²
Race	White vs Non-white
Geographic Region	North America, South/Central America, Western Europe, Eastern Europe, Asia, Other
Number of prior csDMARDs	≤ 1 vs > 1
Number of prior biologic therapies	0 vs ≥ 1
Number of prior anti-TNFs	0 vs ≥ 1
hsCRP at Baseline	< 3 vs ≥ 3 mg/L
Extent of psoriasis at Baseline	≥ 3% BSA vs < 3% BSA
Duration of PsA	≤ 5, > 5 and ≤ 10, > 10 years
Concomitant csDMARD at baseline	Any csDMARD 
 • Any MTX 
 ○ MTX alone ○ MTX and other csDMARD • csDMARD other than MTX None

In addition, subgroup analysis will be conducted for the secondary endpoints by number of prior biologics therapies (0 vs ≥ 1). Similar analysis will be provided.

9.0 Safety Analyses

9.1 General Considerations

Safety data will be summarized for the safety population. For the safety analysis, subjects are assigned to a treatment group based on the treatment actually received, regardless of the treatment randomized. A subject's actual treatment will be determined by the most frequent dose regimen received.

There are two sets of planned safety analysis: safety analysis for Period 1, and long-term safety analysis.

Safety Analysis for Period 1

Standard safety analysis by the actual treatment groups of risankizumab 150 mg and placebo will be performed on safety data up to Week 24. No protocol-defined treatment switching will occur prior to these time points.

The standard safety analyses will include reporting of adverse events (AEs), laboratory, and vital signs measurements. Frequency tables of subjects with treatment-emergent adverse events (TEAEs) by system organ class (SOC) and by preferred term (PT) as in the Medical Dictionary for Regulatory Activities (MedDRA) dictionary will be provided by treatment group. All continuous laboratory parameters and vital signs variables at each visit will also be summarized by actual treatment group. Frequency tables of subjects meeting criteria for potentially clinically significant vital sign values and for potentially clinically significant laboratory values will be provided by treatment group.

Long-Term Safety Analysis

Long-term safety analysis will be performed on all cumulative safety data in Period 1 and Period 2 up to data cutoff date for any interim lock as deemed appropriate and final lock. Long-term safety analyses that account for protocol-defined treatment switching include reporting of AE rate adjusted by cumulative exposure, descriptive summary in laboratory parameters and vital sign variables, and rate of potentially clinically significant laboratory and vital signs values.

To adjust for potentially different follow-up time between treatment groups, exposure-adjusted event rate (EAER) will be provided for long term safety analysis. The EAER will be presented for Any Risankizumab group by actual treatment received at the time of AE. The Any Risankizumab group includes all subjects who received risankisumab 150 mg, including those who started on risankizumab 150 mg at randomization and who switched from placebo to risankizumab 150 mg.

For EAER calculation, the numerator will be the total number of AEs reported for the event (i.e., a subject can contribute more than one event to the numerator) and the denominator will be the total exposure time among subjects under the treatment group. The number of AEs reported (numerator), the total number of years of study drug exposure (denominator, calculated as total number of days exposed to study drug (i.e., last dose date – first dose date + 140 days) for all treated subjects divided by 365.25), and the exposure-adjusted AE event rate per 100 patient-years calculated as $(\text{[numerator (number of AEs)/denominator]}) \cdot 100$ will be presented for each treatment group.

All continuous laboratory parameters and vital signs variables at each visit will be summarized by actual treatment group sequence defined as follows.

1. Placebo → Risankizumab 150 mg
2. Risankizumab 150 mg → Risankizumab 150 mg

Frequency tables and listings of subjects meeting criteria for potentially clinically significant vital sign values and for potentially clinically significant laboratory values will be provided for Any Risankizumab group by actual treatment received at the time of event. Missing safety data will not be imputed.

